9.4.2.1 Dose Reduction Schedule for Intolerable Toxicities

Lenvatinib dose reductions occur in succession based on the previous level (18, 14, 10, 8, and 4 mg/day) as shown in the table below:

Table 3 Dose Reductions for Lenvatinib in Combination With 5 mg Everolimus

Current Dose (QD)	Dose Reduction ^a
18 mg	14 mg QD
14 mg	10 mg QD
10 mg	8 mg QD
8 mg	4 mg QD
a: Subjects in either arm will be allowed a maximum of 3 lenvatinib dose reductions for lenvatinib-related toxicity.	

Note: Subjects in either arm will be allowed a maximum of 3 lenvatinib dose reductions for lenvatinib-related toxicity.

At every dose change, the investigator or a designee will call the Interactive Voice and Web Response System (IxRS) to register the subject's visit (see the IxRS Manual for further instructions). At each of these postrandomization visits, the investigator will select the subject's appropriate treatment dose in accordance with the protocol. As of 01 Oct 2020, the IxRS will be discontinued. Refer to the revised Pharmacy Manual for complete instructions.

9.4.2.2 Management of Hypertension

Hypertension is a recognized side effect of treatment with drugs inhibiting VEGF signaling. Investigators should therefore ensure that subjects enrolled to receive treatment with lenvatinib have BP of $\leq 150/90$ mmHg at the time of study entry and, if known to be hypertensive, have been on a stable dose of antihypertensive therapy for at least 1 week before Cycle 1/Day 1. Early detection and effective management of hypertension are important to minimize the need for lenvatinib dose interruptions and reductions.

Antihypertensive agents should be started as soon as elevated BP (systolic BP ≥ 140 mmHg or diastolic BP ≥ 90 mmHg) is confirmed on 2 assessments a minimum of 30 minutes apart. One BP assessment is defined as the mean value of 3 measurements at least 5 minutes apart. After the data cutoff for the primary analysis, one BP assessment is defined as the mean value of 2 measurements at least 5 minutes apart. The choice of antihypertensive treatment should be individualized to the subject's clinical circumstances and follow standard medical practice. For previously normotensive subjects, appropriate antihypertensive therapy should be started when systolic BP ≥ 140 mmHg or diastolic BP ≥ 90 mmHg is first observed on 2 assessments a minimum of 30 minutes apart. For those subjects already on antihypertensive medication, treatment modification may be necessary if hypertension persists.

Lenvatinib should be withheld in any instance where a subject is at imminent risk to develop a hypertensive crisis or has significant risk factors for severe complications of uncontrolled hypertension (eg, BP $\geq 160/100$ mmHg, significant risk factors for cardiac disease, intracerebral hemorrhage, or other significant co-morbidities). Once the subject has been on the same hypertensive medications for at least 48 hours and the BP is controlled, lenvatinib should be resumed as described below.

During the Treatment Period, subjects with systolic BP ≥ 160 mmHg or diastolic BP ≥ 100 mmHg must have their BP monitored on Day 15 or more frequently as clinically indicated until systolic BP has been ≤ 150 mmHg and diastolic BP has been ≤ 95 mmHg for 1 treatment cycle (ie, 56-day cycle). If a repeat event of systolic BP ≥ 160 mmHg or diastolic BP ≥ 100 mmHg occurs, the subject must resume the Day-15 evaluation until systolic BP has been ≤ 150 mmHg and diastolic BP has been ≤ 95 mmHg for 1 treatment cycle (ie, 56-day cycle).

The following guidelines should be followed for the management of systolic BP ≥ 160 mmHg or diastolic BP ≥ 100 mmHg confirmed on repeat measurements after 30 minutes:

1. Continue lenvatinib and institute antihypertensive therapy for subjects not already receiving this.

2. For those subjects already on antihypertensive medication, the dose of the current agent may be increased, if appropriate, or 1 or more agents of a different class of antihypertensive should be added.
3. If systolic BP ≥ 160 mmHg or diastolic BP ≥ 100 mmHg persists despite maximal antihypertensive therapy, then lenvatinib administration should be interrupted. It should be restarted at 1 dose level reduction only when systolic BP ≤ 150 mmHg and diastolic BP ≤ 95 mmHg and the subject has been on a stable dose of antihypertensive medication for at least 48 hours.
 - If systolic BP ≥ 160 mmHg or diastolic BP ≥ 100 mmHg recurs on the first dose reduction despite optimal management of hypertension with antihypertensive medications (either by dose increase or the addition of a different class of antihypertensive), then lenvatinib administration should be interrupted. It should be restarted at an additional dose reduction only when systolic BP ≤ 150 mmHg and diastolic BP ≤ 95 mmHg and the subject has been on a stable dose of antihypertensive medication for at least 48 hours.
 - If systolic BP ≥ 160 mmHg or diastolic BP ≥ 100 mmHg recurs on the second dose reduction despite optimal management of hypertension with antihypertensive medications (either by dose increase or the addition of a different class of antihypertensive), then lenvatinib administration should be interrupted. It should be restarted at a third dose reduction only when systolic BP ≤ 150 mmHg and diastolic BP ≤ 95 mmHg and the subject has been on a stable dose of antihypertensive medication for at least 48 hours.
 - Additional dose reduction should be discussed with the sponsor.

The following guidelines should be followed for the management of Grade 4 hypertension (life-threatening consequences):

1. Institute appropriate medical management
2. Discontinue study treatment

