Lenvatinib Dose Reduction Schedule For Intolerable Toxicities

Lenvatinib dose reductions occur in succession based on the previous dose level (18, 14, 10, 8, and 4 mg/day), as shown in the table below.

Dose Reductions for Lenvatinib in Combination with 5 mg Everolimus

Current Dose (QD)	Dose Reduction
18 mg	14 mg QD
14 mg	10 mg QD
10 mg	8 mg QD
8 mg	4 mg QD

MANAGEMENT OF HYPERTENSION

Hypertension is a recognized side effect of treatment with drugs inhibiting VEGF signaling. Investigators should therefore ensure that subjects enrolled to receive treatment with lenvatinib have BP of $\leq 150/90$ mmHg at the time of study entry and, if known to be hypertensive, have been on a stable dose of antihypertensive therapy for at least 1 week before Cycle 1/Day 1. Early detection and effective management of hypertension are important to minimize the need for lenvatinib dose interruptions and reductions.

Antihypertensive agents should be started as soon as elevated BP (systolic BP ≥ 140 mmHg or diastolic BP ≥ 90 mmHg) is confirmed on 2 assessments a minimum of 30 minutes apart. One BP assessment is defined as the mean value of 3 measurements at least 5 minutes apart. After the data cutoff for the primary analysis, one BP assessment is defined as the mean value of 2 measurements at least 5 minutes apart. The choice of antihypertensive treatment should be individualized to the subject’s clinical circumstances and follow standard medical practice. For previously normotensive subjects, appropriate antihypertensive therapy should be started when systolic BP ≥ 140 mmHg or diastolic BP ≥ 90 mmHg is first observed on 2 assessments a minimum of 30 minutes apart. For those subjects already on antihypertensive medication, treatment modification may be necessary if hypertension persists.

Lenvatinib should be withheld in any instance where a subject is at imminent risk to develop a hypertensive crisis or has significant risk factors for severe complications of uncontrolled hypertension (eg, BP $\geq 160/100$ mmHg, significant risk factors for cardiac disease, intracerebral hemorrhage, or other significant co-morbidities). Once the subject has been on the same hypertensive

medications for at least 48 hours and the BP is controlled, lenvatinib should be resumed as described below.

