9.5.1.4.4 VITAL SIGNS AND WEIGHT MEASUREMENTS

Vital sign measurements (ie, systolic and diastolic BP [mmHg], pulse [beats per minute], respiratory rate [per minute], body temperature [in centigrade]), and weight (kg) will be obtained at the visits designated in the Schedule of Procedures/Assessments ([Table 6](#)) by a validated method. Blood pressure and pulse will be measured after the subject has been resting for 5 minutes. All BP measurements should be performed on the same arm, preferably by the same person. One BP assessment is defined as the mean value of 3 measurements at least 5 minutes apart. After the data cutoff for the primary analysis, one BP assessment is defined as the mean value of 2 measurements at least 5 minutes apart.

Vital sign measurements (resting BP [including date and time of measurement], HR, RR and body temperature) will be obtained, excluding weight at the visits designated in the Schedule of Assessments After the Data Cutoff for the Primary Analysis ([Table 7](#)).

For subjects with an elevated BP (systolic BP ≥ 140 mm Hg or diastolic BP ≥ 90 mmHg), confirmation should be obtained by performing 2 assessments a minimum of 30 minutes apart.

Subjects with systolic BP ≥ 160 mmHg or diastolic BP ≥ 100 mmHg must have their BP monitored every 2 weeks (on Day 1 and Day 15 or more frequently, as clinically indicated) until systolic BP has been ≤ 150 mmHg and diastolic BP has been ≤ 95 mmHg for 1 treatment cycle (ie, 56-day cycle). A diary will be provided to the subject to capture the BP evaluations between study visits. See subsection for management of hypertensive subjects ([Section 9.4.2.2](#)).

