- e. Assessments will include vital signs (resting BP [including date and time of measurement], HR, RR and body temperature), weight, and height. Height will be measured at the Screening visit only. One BP assessment is defined as the mean value of 3 measurements at least 5 minutes apart. An elevated BP assessment (ie, systolic BP ≥140 mmHg or diastolic BP ≥90 mmHg) should be confirmed by a repeat assessment after a minimum of 1 hour. Subjects with systolic BP ≥160 mmHg or diastolic BP ≥100 mmHg must have their BP monitored every 2 weeks (on Day 1 and Day 15 or more frequently, as clinically indicated) until systolic BP has been ≤150 mmHg and diastolic BP has been ≤95 mmHg for 3 consecutive months. A diary will be provided to the subject to capture the blood pressure evaluations between study visits. See subsection for [management of hypertensive subjects](#).
Note: During Cycle 3 and subsequent cycles, subjects may return to the clinic for the Day 15 visit if BP monitoring testing is required as specified above. The Day-15 visit is mandatory in Cycles 1 and 2.
- f. A comprehensive physical examination (including a neurological examination) will be performed at the Screening or Baseline Visits, on Cycle 1/Day 15, on Day 1 of each subsequent cycle, and at the Off-Treatment assessment. A symptom-directed physical examination will be performed on C1D1

and at any time during the study, as clinically indicated.

- g. Required if screening physical examination was performed >7 days prior to C1D1.
- h. Single 12-lead ECG. Subjects are suggested to be in the recumbent position for a period of 5 minutes prior to obtaining ECG.
- i. An echocardiogram or MUGA scan to assess LVEF will be performed at Screening and as clinically indicated.
- j. A serum or urine pregnancy test will be performed at the Screening Visit, at the Baseline Visit (or within 72 hours prior to the first dose of study drug), at Day 1 of every cycle (starting with Cycle 2), and at the Off-Treatment assessment in women of childbearing potential (ie, premenopausal and perimenopausal women who have been amenorrheic for less than 12 months).

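### Hypertension and proteinuria rules give conflicting instructions: what to do at BP 160/100, how long to wait before confirming raised BP, and when extra monitoring ends

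*Protocol*

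**What the plan says.** **Action at BP 160/100.** Section 9.4.2.2 states: "Lenvatinib should be withheld in any instance where a subject is at imminent risk to develop a hypertensive crisis or has significant risk factors". The factors meant are those for "severe complications of uncontrolled hypertension (eg, BP $\geq 160/100$ mmHg", followed by other examples. The synopsis repeats the rule ("Lenvatinib should be withheld in any instance where a subject is at imminent risk to develop a hypertensive crisis"). The numbered guideline that follows covers systolic ≥160 or diastolic ≥100 mmHg confirmed after 30 minutes. Its first step is "Continue lenvatinib and institute antihypertensive therapy for subjects not already receiving this". Interruption comes at the third step, if the level "persists despite maximal antihypertensive therapy, then lenvatinib administration should be interrupted". The synopsis carries the same steps.

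**Confirming BP ≥140/90.** In section 9.4.2.2, antihypertensive agents start once elevated BP "is confirmed on 2 assessments a minimum of 30 minutes apart"; the synopsis agrees. Section 9.5.1.4.4 says "confirmation should be obtained by performing 2 assessments a minimum of 30 minutes apart". Table 6 footnote e says an elevated assessment "should be confirmed by a repeat assessment after a minimum of 1 hour".

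**End of extra monitoring.** After BP ≥160/100, the synopsis and sections 9.4.2.2 and 9.5.1.4.4 stop the additional checks once BP has been controlled for one treatment cycle, specified as 56 days. Table 6 footnote e requires 3 consecutive months. For dipstick protein ≥2+, the synopsis and section 9.4.2.3 use the 56-day cycle, and Table 6 footnote l uses 3 consecutive months.

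**The concern.** Two sites that both follow the protocol can manage the same recognised toxicity differently. One may hold lenvatinib at 160/100 while the other continues it. One may confirm at 30 minutes, which does not meet Table 6. One may stop fortnightly checks weeks before the other. This is first a matter of consistent patient safety. In a trial that compares starting doses at about 100 sites, the first inconsistency could also add site differences in lenvatinib holds, reductions and dose intensity.

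No effect on the primary endpoints is claimed. SAP Table 8 places systolic ≥160 or diastolic ≥100 mmHg at Grade 3, so an adverse event graded that way counts in the primary safety endpoint whether or not drug is held.

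**Working it through.** No sample size, power or alpha figure is involved. The check compares the passages and converts months to days.

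**1. Action at 160/100.** Take a subject confirmed at 165/105 mmHg who is not on antihypertensives.
- The withholding paragraph is conditional on imminent crisis risk or significant risk factors, but BP at this level is itself one of its examples. On that reading, lenvatinib is held.
- Step 1 of the guideline applies to the same reading. Lenvatinib is continued and antihypertensive therapy started.
- The withholding paragraph refers to resumption as set out below it. The text below describes restart only after maximal therapy has failed, so a subject held under the first paragraph has no matching restart instruction.

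This part carries no period label and so applies before and after the primary-analysis cutoff.

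**2. Confirmation interval, BP ≥140/90.**

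| Place | Minimum wait |
|---|---|
| Synopsis, 9.4.2.2, 9.5.1.4.4 | 30 minutes |
| Table 6 footnote e | 60 minutes |

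A repeat at 30 to 59 minutes confirms under the first row and not under the second. A repeat at 60 minutes or later satisfies both.

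**3. End of extra monitoring.**

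| Test | 56-day cycle | 3 consecutive months |
|---|---|---|
| BP | Synopsis, 9.4.2.2, 9.5.1.4.4 | Table 6 footnote e |
| Dipstick | Synopsis, 9.4.2.3 | Table 6 footnote l |

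Which subjects does each rule reach?
- Section 9.4.6 and Table 6 set 28-day cycles in the Randomization Phase; 56-day cycles exist only after the cutoff.
- The BP rule in 9.4.2.2 is placed in the Treatment Period. Section 9.1.2.1 starts that period at the first dose and runs it in 28-day cycles. The synopsis also uses the term for the 56-day cycles after the cutoff. The term therefore spans both periods.
- Section 9.4.2.2 labels its BP-averaging rule as applying after the cutoff, but gives the end-rule no such label. Sections 9.4.2.3 and 9.5.1.4.4 give their end-rules none either.
- Section 9.5.1.4.4 pairs the 56-day rule with fortnightly checks on Days 1 and 15. Those two days cover a 28-day cycle; a 56-day cycle would also need Days 29 and 43.
- Table 6 footnotes e and l, which govern the 28-day phase, refer the reader to the hypertension and proteinuria subsections that hold the 56-day rule.

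As written, both end-rules reach a subject before the cutoff.

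**Size of the gap.** The protocol does not define a month here, so a range is shown:
- Assuming one month is one 4-week cycle: 3 × 28 = 84 days.
- Borrowing the month length in SAP section 8.4.1: 3 × 30.4375 = 91.3 days.
- Difference from 56 days: 84 − 56 = 28.0 days; 91.3 − 56 = 35.3 days, so 4.0 to 5.0 weeks.
- As a share of the longer rule: 28.0/84 = 33%; 35.3/91.3 = 39%.
- Two-week intervals: 56/14 = 4.0 against 84/14 = 6.0 or 91.3/14 = 6.5, so 2.0 to 2.5 fewer per episode.

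**The case against.** The best defence concerns the monitoring end-rules. A subject before the cutoff has no 56-day cycle, and the synopsis states that the Treatment Period after the cutoff consists of such cycles. Table 6 carries its own 3-month rule for the Randomization Phase. Table 7 footnotes b and h have no end-rule and send the reader to the hypertension and proteinuria sections. One rule per period is then a natural reading, and the fault shrinks to a missing label. This is persuasive about intent, and the intent is accepted as probable. It does not limit the text, because the term covers both periods, two of the sections carry no period label, and Table 6 cross-refers to the same subsections.

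On the action at 160/100, the two paragraphs can be read as an exception for high-risk subjects and a general default. That is why the fault is called ambiguity. It remains because BP at that very level is listed as an example of the exception.

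On confirmation, both figures are minimums and a 1-hour wait meets both. That stands, and the practical difference is confined to repeats at 30 to 59 minutes.

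Two further limits stand. The SAP month length was written for durations before randomization and is borrowed here. The documents give no cutoff date, and few subjects before the cutoff may have been managed under the 56-day text, since this protocol version was signed in September 2020.

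**Conclusion.** The concern holds. The current protocol text gives an ambiguous action at BP 160/100, two minimum confirmation intervals (30 and 60 minutes) for BP ≥140/90, and two end-rules for extra BP and dipstick monitoring. The end-rules differ by 28.0 to 35.3 days, or 33% to 39% of the longer one. That range rests on the two assumed month lengths and on both rules reaching the same subject before the cutoff, which the wording allows though probably does not intend. For proteinuria, only the monitoring end-rule conflicts. The number of subjects affected and any effect on dose holds cannot be derived from the documents. The point should be corrected for consistent patient safety; it changes no sample size, power or alpha.

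**What to change.** Reconcile sections 9.4.2.2, 9.4.2.3 and 9.5.1.4.4, the synopsis, and Table 6 footnotes e and l, so that each threshold has one action, one confirmation interval and one monitoring end-rule. State which rules apply before and which after the primary-analysis cutoff, as 9.4.2.2 already does for BP averaging. Make the resumption reference in the withholding paragraph point to text that covers that situation. Which text stands is for the sponsor's clinical team to decide.

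The cost is protocol wording, by amendment or clarification letter, and a notice to sites. There is no statistical cost.

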9.4.2.3 Management of Proteinuria

Regular assessment of proteinuria should be conducted as detailed in the Schedule of Procedures/Assessments (Table 6) and the Schedule of Assessments After the Data Cutoff for the Primary Analysis (Table 7). Guidelines for assessment and management of proteinuria:

1. Grading will be based on the 24-hour urinary protein result. Management of lenvatinib administration will be based on the grade of proteinuria according to instructions contained in Table 2, "Dose Modification Guidelines for Lenvatinib-Everolimus Combination Treatment-Related Toxicity,"
2. A 24-hour urine collection (within 72 hours) to verify the grade of proteinuria for protein quantitation is required in the following situations:
 - The first (initial) occurrence of $\geq 2+$ proteinuria on urine dipstick while on study drug

- A subsequent increase in severity of urine dipstick proteinuria occurring on the same lenvatinib dose level
 - When there has been a lenvatinib dose reduction and at the new dose level the urine protein dipstick result is 2+, 3+, or 4+
3. Urine dipstick testing for subjects with proteinuria $\geq 2+$ should be performed every 2 weeks (or more frequently as clinically indicated) until the results have been 1+ or negative for 1 treatment cycle (ie, 56-day cycle).

9.4.2.4 Management of Diarrhea

An antidiarrheal agent should be recommended to the subject at the start of study treatment and subjects should be instructed and educated to initiate antidiarrheal treatment at the first onset of soft bowel movements. The choice of antidiarrheal agent should be individualized to the subject's clinical circumstances and follow standard medical practice. If signs/symptoms of diarrhea persist despite optimal medical management, instructions contained in [Table 2](#), "Dose Modification Guidelines for Lenvatinib-Everolimus Combination Treatment-Related Toxicity," should be followed.

9.4.2.5 Management of Non-Infectious Pneumonitis

Non-infectious pneumonitis is a recognized class effect of rapamycin derivatives, including everolimus. Non-infectious pneumonitis was described in 19% of subjects taking everolimus ([AFINITOR® Package Insert](#)). Some cases were severe and on rare occasions, a fatal outcome was observed. Investigators should therefore consider a diagnosis of non-infectious pneumonitis in subjects presenting with non-specific respiratory signs and symptoms and in whom infectious, neoplastic and other non-medicinal causes have been excluded by means of appropriate investigations.

Subjects who develop radiological changes suggestive of non-infectious pneumonitis and have few or no symptoms (CTCAE Grade 1) may continue study dosing without dose adjustments.

- If symptoms are moderate (CTCAE Grade 2):
 - Lenvatinib-everolimus combination therapy should be interrupted and the use of corticosteroids may be indicated until symptoms abate (resolved to CTCAE Grade 0-1) and may then be restarted at the same doses prior to study treatment interruption.
 - If Grade 2 non-infectious pneumonitis recurs despite optimal management, then lenvatinib-everolimus combination therapy administration should be interrupted and the use of corticosteroids may be indicated until symptoms abate (resolved to CTCAE Grade 0-1).
- If symptoms are severe (CTCAE Grade 3):
 - Lenvatinib-everolimus combination therapy should be interrupted and the use of corticosteroids may be indicated until clinical symptoms resolve (to CTCAE

Grade 0-1). Investigators will decide the probability of the event being related to 1 or both drugs as to whether dose modification of 1 or both drugs is required.

- If symptoms are life-threatening (CTCAE Grade 4):
 - Everolimus should be discontinued. Investigators will decide the probability of the event being related to 1 or both drugs as to whether discontinuation of 1 or both drugs is required.

